assessed using a widely employed salivary testing technique. Briefly, we will ask that participants chew a paraffin tablet (Orion Diagnostica) for 5 minutes after which the participant will be asked to spit into a 50mL tube until 5mL of saliva is collected. We have experience with this non-invasive assessment⁶⁹, with the assessment taking no longer than 5-10 minutes overall and presenting no greater than minimal risk. Other secondary outcomes are necessary to measure to ensure we can properly control for confounding. Dietary composition will be assessed via 3 phone-based dietary recalls during the run-in phase, and again during the final two weeks of the study. We will use these dietary recalls collected during the run-in period to develop personalized 3-day meal plan to standardize individual dietary behavior prior to stool sample collection. Employing dietary recalls at these time points will also allow us to adequately statistically control for participants' dietary changes—changes which, if not controlled, might confound study results.^{70,71} Physical activity will be measured for the duration of the study using the Fitbit Inspire 2 smartwatch that uses accelerometry to measure physical activity metrics such intensity, steps, etc. Finally, anthropometric outcomes will include height, weight, and body composition. These measures, along with the other secondary outcomes aside from PA and Dietary composition, will be measured at the end of the 3-week run-in phase, and at the end of the 4th and 8th study weeks.

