5.2 **Study Procedures:** All eligible and consented participants will complete a 3-week run-in phase during which baseline outcome assessments will be performed. During run-in weeks 1 and 2, participants will wear a Fitbit Inspire 2 smartwatch and complete three unannounced dietary recalls. During the run-in week 3 (see table below), participants will consume their 3-day standardized meal plan on days three through five, obtain a fecal sample, and complete a study assessment visit. To quantify compliance with the 3-day meal plan, participants will be provided with a paper checklist of all foods to be consumed, and will be asked to indicate which foods were consumed and to document any deviation. The study assessment visit will include a fasting blood draw, blood pressure in triplicate, weight measure and body fat assessment in duplicate, and a saliva sample. Following successful completion of all measures, participants will then be randomized into one of the two study groups using PROC PLAN (SAS 9.4) and a 1:1 allocation ratio.

Group 1 (Experimental group): Participants will complete 3 treadmill walking sessions/week (24 total sessions) over 8 weeks at or around their home or in-person within the Epidemiology Clinical Research Center. Each walking sessions will be 30 min in duration during intervention weeks 1

MEDICAL PROTOCOL (HRP-590)

PROTOCOL TITLE: Exercise and the Gut Microbiome R21

VERSION DATE: 05/11/2022

through 4 and 45 min during intervention weeks 5 through 8. Notably, this exercise dose (i.e., intensity x session duration x weekly frequency x intervention length) is equivalent to, or greater than, that employed in most existing human studies of exercise and the gut microbiome in addition to the exercise dosage observed necessary to yield meaningful cardiometabolic changes.⁷² Therefore, while the dose is 'modest', it reflects what is relevant in real-world interventions and appropriate for overweight or obese sedentary individuals.

During week 4, participants will again consume their 3-day standardized meal plan, obtain a fecal sample, and complete a study assessment visit (same measures as described above for the 3-week run-in, except no fasting blood draw will be taken).

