During weeks 7 and 8, participants will complete 3 unannounced phone-based dietary recalls. During week 8, participants will again consume their 3-day standardized meal plan, obtain a fecal sample, and complete a study assessment visit (same measures as described above in run-in week 3).

Table 1. Timing of Data Collection events during the 3-Week Run-In and Intervention Weeks 4 & 7/8.

Day 1	Day 2	Day 3	Day 4	Day 5	Day 6	Day 7
				Stool (pm)*	Stool (am)*	Stool
		Standard Diet Day1	Standard Diet Day2	Standard Diet Day3		
						Assess. Visit

**Preferred timing stool collection is the evening of Day 5 or morning of Day 6, though anytime in the Day 5 – 7 window is acceptable.*

Group 2 (Control group): Participants will be asked to maintain their usual PA during the initial 8-week intervention period but will undergo all data collection procedures as outlined above for the experimental group.

Expanded Data Collection Procedures: We have two **Primary Outcomes**.

The first primary outcome is changes to the gut microbiome, assessed via metagenomic sequencing, from pre- to post-intervention (**Specific Aim 1**). The Shannon Index will be our primary indicator for changes in gut microbiota composition. Participants will use the OMNIgene-Gut stool collection kit to obtain their fecal samples collected at baseline, week 4 and

MEDICAL PROTOCOL (HRP-590)

PROTOCOL TITLE: Exercise and the Gut Microbiome R21

VERSION DATE: 05/11/2022

week 8. The home-collected samples will be returned to our lab within 30 days. DNA will be extracted from the stool samples using the 96 well plate Mo Bio Power soil kit on an Epmotion robot and eluted into 50ul aliquots. Each extraction will contain negative and positive controls representing defined bacterial communities (Zymo; Irvine, CA). DNA will be quantified using Quant-it and stored at -80°C. Metagenomic libraries will be prepared at the *UMN Genome Center* (see 'Facilities' document) using the Nextera XT kit (Illumina; San Diego, CA) and barcoded. DNA libraries will be denatured with NaOH and diluted to 8-12 pM in Illumina's HT1 buffer, spiked with 1% PhiX and a HiSeq 1x100 cycle v3 kit Illumina HiSeq, with an expected output of at least 0.5 million total sequences per sample. This approach has been shown to be valid⁵⁴ and represents an approach that can address both gut microbial taxonomy and community functional content at a cost similar to 16S studies.

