collected. The oral microbiome will be assessed using a widely employed salivary testing technique. Participants will be asked to drool into a 50mL tube until 5mL of saliva is collected. For participants that are having difficulty generating saliva, we will ask those participants chew a small piece of orthodontic wax for 5 minutes and then drool into the 50mL tube. We have experience with this non-invasive assessment⁶⁹, with the assessment taking no longer than 5-10 minutes overall and presenting no greater than minimal risk. Other secondary outcomes are necessary to measure to ensure we can properly control for confounding. Dietary composition will be assessed via 3 phone-based dietary recalls. These recalls will be performed on 2 weekdays and 1 weekend day by trained interviewers. Assessment of diet on multiple days allows us to capture the individual variation in participants' diets.⁷¹ We will use these dietary recalls to develop personalized 3-day meal plan to standardize individual dietary behavior prior to stool sample collection. Although randomization should lead to approximately balanced groups with respect to diet, employing dietary recalls at these time points will allow us to adequately statistically control for participants' dietary changes—changes which, if not controlled, might confound study results.^{70,71} Physical activity will be measured during the duration of the study using the Fitbit Inspire 2 smartwatch. Finally, anthropometric outcomes will include height measured using a Seca stadiometer (Seca; Hamburg, Germany), with weight and body composition measured using the Tanita TBF-300a Body Composition Analyzer (Tokyo, Japan).

To collect blood samples and saliva samples as well as body weight, body fat percentage, and blood pressure, we are proposing to employ the following procedures in the designated settings while following all necessary COVID-19 precautions:

Setting: Baseline, week 4, and week 8 visits will occur in the Epidemiology Clinical Research Center (ECRC). We will follow all UMN, OVPR and ECRC approved guidelines for conducting research during the COVID-19 pandemic.

COVID-19 Screening: Participants will complete the OVPR-approved ECRC COVID-19 phone screener the day prior to their visit. Prior to entering the ECRC, participants will call the study coordinator and complete the screening questionnaire again. Upon entry into the building, study staff will assess the participant's temperature.

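### Follow-up diet recalls may fall on the week-8 meal-plan days while baseline recalls cannot, so measured dietary change may be understated

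*Combined protocol and SAP*

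**What the plan says.** The baseline sequence is in section 5.2: "During run-in weeks 1 and 2, participants will wear a Fitbit Inspire 2 smartwatch and complete three unannounced dietary recalls". In run-in week 3, "participants will consume their 3-day standardized meal plan on days three through five". Recalls come first and the plan afterwards.

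The follow-up sequence is in the same section: "During weeks 7 and 8, participants will complete 3 unannounced phone-based dietary recalls", and then "During week 8, participants will again consume their 3-day standardized meal plan, obtain a fecal sample, and complete a study assessment visit". Table 1 gives the day 3 to 5 layout for the plan at follow-up as well. Section 3.2 confirms the recall window, saying that diet is assessed "again during the final two weeks of the study".

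On where the plan comes from, section 3.2 says: "We will use these dietary recalls collected during the run-in period to develop personalized 3-day meal plan to standardize individual dietary behavior".

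Two limits on recall timing are stated. Section 5.2 sets the day mix: "These recalls will be performed on 2 weekdays and 1 weekend day by trained interviewers". Section 16.5 says that calls are made only at times the participant has offered. Neither excludes plan days.

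On purpose, section 5.2 says that "employing dietary recalls at these time points will allow us to adequately statistically control for" changes in participants' diets, which it regards as a possible source of confounding.

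**The concern.** The two measurement windows are not alike. A baseline recall can only describe free-living diet. A follow-up recall may describe either free-living diet or three days of eating prescribed by the study, and the prescription was developed from that participant's own baseline recalls. A plan-day recall at follow-up therefore partly compares the baseline diet with itself.

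What is at stake is the validity of the dietary-change variable. With three recalls per time point, a single plan-day recall is a third of a participant's follow-up information. The checklist in section 5.2 covers adherence on plan days only, so the recalls are the only planned measure of habitual diet late in the intervention. If diet did shift, in one arm or both, the variable meant to show it could under-record the shift.

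**Working it through.** The plan gives no figure for this overlap, so there is nothing to reproduce. The overlap can be counted from the schedule.

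**Inputs from the protocol**
- Baseline: 3 recalls in run-in weeks 1-2, plan in run-in week 3 (5.2). Plan days inside the recall window: 0.
- Follow-up: 3 recalls in weeks 7-8, that is 14 days; plan on days 3-5 of week 8 (5.2, Table 1). Plan days inside the window: 3 of 14 (21%).
- Day mix: 2 weekdays and 1 weekend day (5.2). Any 14 consecutive days hold 10 weekdays and 4 weekend days.

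**Assumptions not in the protocol**
- Recall days are drawn at random within each day type.
- The day-7 visit falls on a weekday.
- The plan is fully followed and mirrors mean baseline intake.

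**Formulas.** Let w and e be the numbers of weekday and weekend plan days, with w + e = 3.
- Expected share of recalls on plan days: s = (2w/10 + e/4)/3
- Chance of at least one: P = 1 − [C(10−w, 2)/C(10, 2)] × (4−e)/4
- Mean measured change as a fraction of true change: 1 − s

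| Visit day | w, e | s | P | 1 − s |
|---|---|---|---|---|
| Fri | 3, 0 | 0.60/3 = 20.0% | 1 − 21/45 = 53.3% | 80.0% |
| Mon or Thu | 2, 1 | 0.65/3 = 21.7% | 1 − (28/45)(3/4) = 53.3% | 78.3% |
| Tue or Wed | 1, 2 | 0.70/3 = 23.3% | 1 − (36/45)(1/2) = 60.0% | 76.7% |

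Ignoring day type gives nearly the same chance: 1 − C(11,3)/C(14,3) = 54.7%.

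**Individual level.** With k of 3 recalls on plan days, measured change is (1 − k/3) of true change: all of it, two thirds, one third or none for k = 0, 1, 2, 3. The last case is rare. It needs w = 2 and e = 1, and then has chance (1/45)(1/4) = 0.6%.

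**Sensitivity**
- Timing: if every recall fell before the plan began, s = 0 and nothing is lost. If all three fell in week 8 (5 weekdays, 2 weekend days), s = (2w/5 + e/2)/3, which is 40-47%.
- Plan fidelity: if only a fraction c of the true change is masked on a plan day, the measured fraction is 1 − c × s. At c = 0.5, for illustration, this is 88-90% instead of 77-80%.

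**The case against.** The strongest reply is that section 5.2 sets only a window. It puts no recall on a plan day, and a schedule using week 7 and the first two days of week 8 already complies. This stands. A reader might infer that measured dietary change is biased as a matter of fact, but the text permits overlap without requiring it, and random placement is an assumption. What remains is that the protocol has no rule preventing the overlap, although its own baseline schedule avoids it.

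A reader might also infer that the error always runs toward zero. That needs a plan that reproduces baseline intake and is fully followed. The protocol says only that the recalls are used to develop the plan, and it expects deviations, which the checklist records. A plan unlike the usual diet could even show change where there was none. Toward zero is the expected direction, not a certain one.

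A third tempting inference is that microbiome or SCFA effects would be wrongly credited to exercise. The documents do not support this. Section 15.3 regresses the Aim 1 and Aim 2 outcomes on randomized arm. It names no diet covariate: the confounder vector for Aims 1 and 2 is unspecified, and the Aim 3 list is age, sex, race/ethnicity and activity duration. Dietary change after randomization cannot confound assignment; if walking alters diet, that is part of its effect. Both arms follow the same schedule, and diet just before each stool sample is handled separately by the meal plan.

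Nor are the recalls the protocol's test of inclusion criterion 10. That criterion is willingness at enrolment, and the stated uses of the recalls are building the plan and statistical control.

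Finally, plan-day recalls could be removed at analysis if recall and plan dates are both kept. That is true, but it costs data that better scheduling would save.

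**Conclusion.** The concern holds in a limited form. As written, section 5.2 separates recalls from the meal plan at baseline and does not do so at follow-up, and the plan's origin in the run-in recalls gives the resulting error an expected direction.

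Under random placement, full adherence and a plan that mirrors baseline intake, about a fifth of follow-up recalls would cover plan days, more than half of participants would be affected, and mean measured change would shrink by 20-23%. The loss is smaller with weaker adherence and zero if staff already avoid plan days. It could reach 40-47% if recalls were concentrated in week 8.

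The damage is confined to the dietary-change variable, any analysis adjusted for it, and any claim that diet was stable. The unadjusted comparisons of Shannon Index and serum SCFAs by randomized arm are unaffected. The change is still worth making, because the recalls cannot properly serve their stated purpose if some of them record the study's own prescription.

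**What to change.** In sections 5.2 and 3.2, require the follow-up recalls to cover only days before the week-8 meal plan starts, that is week 7 and days 1-2 of week 8, keeping two weekdays and one weekend day. State that any recall found to have covered a plan day is flagged and left out of the dietary-change calculation, and that recall dates and plan dates are both recorded so this can be checked.

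The cost is a sentence in each section and an instruction to the interviewers, with no extra calls. The window shortens from 14 to 9 days (7 + 2). Any nine consecutive days contain at least two weekend days and at least five weekdays, so the day mix remains feasible, though there is less room to fit participants' availability. A participant with an excluded recall will have fewer than three follow-up days, and possibly no weekend day, so that person's estimate will be less precise.

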6.0 Data and Specimen Banking

6.1 **Storage and Access:** We will initially collect data on paper after which we will transfer these data to computer spreadsheets for export to statistical packages, with this data entry conducted separately by two individuals to ensure data integrity. All PHI will be stored in a folder on the University of Minnesota's Box drive which is HIPAA compliant. All paper-based data will be stored in a locked file cabinet within the West Bank Office Building near the PI's office for a minimum of three years after the last participant has completed data collection. We will also store the de-identified electronic data for a minimum of three years on a server within the Division of Epidemiology and Community Health.

Buffy coat and serum from blood draws and saliva from salivary collection will be stored for up to 20 years in the PI's freezers located at the

MEDICAL PROTOCOL (HRP-590)

PROTOCOL TITLE: Exercise and the Gut Microbiome R21

VERSION DATE: 05/11/2022

Epidemiology Clinical Research Center or MoosT 1-355. All NIH procedures and University policies for the protection of confidentiality will be followed. Identifying data will be kept confidential, and only de-identified data will be shared.

6.2 **Data:** We will collect the following data: Serum, plasma, buffy coat, saliva, stool samples, Fitabase activity app data, food recall data, questionnaire data, and anthropometric data. The following data will be banked for future use if the participant consents: Serum, plasma, buffy coat, stool, and saliva. Otherwise, we will properly dispose of these specimens. All data will only be linked via a unique identification number. No identifying information will be included.

6.3 **Release/Sharing:** Materials generated under the project will be disseminated in accordance with University and NIH policies. Depending on such policies, materials may be transferred to others under the terms of a material transfer agreement. Access to databases and associated software tools generated under the project will be available for educational, research, and non-profit purposes. Such access will be provided using web-based applications, as appropriate. Publication of data shall occur during the project, if appropriate, or at the end of the project, consistent with normal scientific practices. Research data which documents, supports and validates research findings will be made available after the main findings from the final research data set have been accepted for publication. Such research data will be redacted to prevent the disclosure of personal identifiers.

7.0 Sharing of Results with Participants

7.1 **Sharing Results:** Following the conclusion of the study, we will share with each participant their anthropometric (weight, waist circumference) and cardiometabolic data (fasting insulin/glucose, triglycerides, cholesterol levels, and blood pressure) collected during the 2-week run-in visit/baseline fasting visit and following the 4th and 8th weeks. We will share these data in a personalized letter to each participant. Further, we will provide participants with an overall aggregated summary of the study's observations and/or any published manuscripts.

7.2 **Sharing Genetic Results:** N/A

7.2.1 **Disclosure of Results:** N/A

7.2.2 Returning Results to Participants: N/A

Aggregate or individual results: N/A

Laboratory results: N/A

Plan for return of results to participants: N/A

Types of results to be returned to participants: N/A

7.2.3 Future analysis of genotypes: N/A

8.0 Study Population

8.1 Inclusion Criteria:

- (1) 30-64 years old.
- (2) Classified as overweight or obese with BMI >25.0kg/m², no upper limit
- (3) Documentation* of a PreD diagnosis within one year of enrollment by physician or primary care provider based on lab tests showing a fasted blood glucose of 100-125 mg/dL, a 2-hour oral glucose tolerance test of 140-199 mg/dL, or an HbA1c level of 5.7%-6.4%⁷⁶; OR a study screening lab value of HbA1C within the afore mentioned range.
- (4) Currently engaged in <100 min/week of PA—confirmed via the Modifiable Activity Questionnaire.⁷⁷
- (5) No exercise contraindications as assessed by the Physical Activity Readiness Questionnaire (PAR-Q)⁷⁸—this Questionnaire involves seven “yes” or “no” questions regarding an individual’s health status, with answering “yes” to any one of these questions requiring a prospective participant to acquire a written doctor’s note stating they can safely participate in the trial’s exercise intervention. They would not be enrolled until this doctor’s note is received.
- (6) No self-reported physical/mental disabilities or gastrointestinal conditions.
- (7) No antibiotic usage within the last 45 days.
- (8) Stable weight over the last 6 months (<10% change).
- (9) Not currently pregnant, planning to become pregnant, or currently breastfeeding.
- (10) Willing to maintain current dietary and exercise habits, aside from any changes to be made per the study exercise protocol.

*Note: Documentation can include either a print out or screen shot of the lab value illustrating eligibility, along with the date of the test and the participant’s name. If a hard copy is provided, the date and name

MEDICAL PROTOCOL (HRP-590)

PROTOCOL TITLE: Exercise and the Gut Microbiome R21

VERSION DATE: 05/11/2022

will be redacted.

8.2 Exclusion Criteria:

- (1) Individuals <30 or >64: younger individuals may have not yet reached physiological maturity and in whom PreD prevalence is low; older individuals are more likely to have contraindications to PA and other comorbidities.
- (2) BMI< 25kg/m². No Upper limit.
- (3) Individuals with an HbA1c level <5.7% or >6.4%.
- (4) Currently engaged in ≥100 min/wk of PA.
- (5) Individuals with contraindications to exercise participation as indicated by the PAR-Q.
- (6) A self-reported physical/mental disability that would prevent them from being able to adhere to the intervention.
- (7) A self-reported a gastrointestinal illness or condition.
- (8) Antibiotic use within the last 45 days.⁷⁹⁻⁸¹
- (9) Self-reported use of metformin and/or other medications that could interfere with the primary outcome.
- (10) Unstable weight over the last six months (> 10% change).
- (11) History of bariatric surgery or a history of other medical interventions that would interfere with the primary outcome.
- (12) Currently pregnant or planning to become pregnant during the study period.
- (13) Currently breastfeeding.
- (14) Unwilling to be randomized to a study group.

8.3 Screening: Interested individuals will be asked to complete a red-cap screening questionnaire (sent via email or with study staff over the phone) which will enable staff to pre-review possible participants for eligibility. Everyone who completes a screener will be contacted, and, if needed, screening responses can be clarified.

Those who meet all eligibility criteria can then be scheduled for their consent/first study visit.

Those who *appear* eligible but need to confirm that their HbA1c is within eligibility range will be scheduled to complete a consent/screening visit. At this visit, following completion of the consent/HIPAA form, participants will have their HbA1c tested. To determine their current HbA1c value, we will either use the A1cNOW+® device or collect a 2mL whole blood sample via venipuncture.⁶⁸ Of note, one of these methods will only be employed only after the participant has consented to be screened for the study. Briefly,

MEDICAL PROTOCOL (HRP-590)**PROTOCOL TITLE:** Exercise and the Gut Microbiome R21**VERSION DATE:** 05/11/2022

the A1cNOW+® device will use a small drop of blood obtained from a finger of a prospective participant to determine the individual's HbA1C levels.

This device has been validated against clinical laboratory measurements of HbA1C and is certified by the National Glycohemoglobin Standardization Program for this purpose.⁸⁵ If a venipuncture sample is collected, this sample will be brought to the Advanced Diagnostic Research Laboratory for analysis.

